10.3.1. Investigator's Global Assessment (IGA)

The IGA is a 5-point scale ranging from 0 (clear) to 4 (severe) used by the investigator or trained designee to evaluate the global severity of PN and the clinical response to a treatment (see [Table 10-2](#)).

Table 10-2: Investigator Global Assessment Scale

0	Clear	No nodules
1	Almost Clear	Rare palpable pruriginous nodules
2	Mild	Few palpable pruriginous nodules
3	Moderate	Many palpable pruriginous nodules
4	Severe	Abundant palpable pruriginous nodules

IGA treatment success is defined as 0 (clear) or 1 (almost clear) on the IGA scale and a \geq 2-point reduction from Baseline.

IGA will be collected at Baseline/Day 1, Week 4, Week 8, Week 12, Week 16, Week 20, Week 24 and Early Termination. In case of missing assessment at Baseline, the last available assessment prior study drug administration will be considered as Baseline.

IGA will be summarized as a categorical and continuous variable at each analysis visit. Absolute change from Baseline for the IGA score will also be presented in the summary on the ITT and PP population.

This document is confidential.

The proportion of subjects with IGA success (OC, non-responder, LOCF) will be summarized on the ITT and PP population. It will also be analyzed using non-responder imputation and a Cochran-Mantel-Haenszel (CMH) test adjusted for the randomization strata analysis center and body weight at randomization (< 90 kg, \geq 90 kg). The estimate of treatment unadjusted and strata-adjusted differences with the corresponding two-sided 95% confidence intervals, and p-values from the CMH test will be presented.

Additionally, the proportion of subjects with IGA \leq 2 (Responder) will be presented using missing as non-responder for ITT population up to Week 24.

Line plots for proportion of subject with IGA success using non-responder imputation will be generated for the ITT and PP population.

10.3.2. Prurigo Activity Score (PAS)

The Investigator or designee will use the PAS as an evaluation of the disease. This includes a count of the number of lesions in a representative area and a calculated staging (stage 0 to stage 4) based on the percentage of lesions with excoriations/crusts and healed lesions compared to all lesions.

Following items will be summarized at Baseline, Week 4, Week 8, Week 12, Week 16, Week 20, and Week 24:

- PAS item 1a/1b: Type of prurigo
- PAS item 2: Number of pruriginous lesions
- PAS item 3: Affected area(s)
- PAS item 4: Number of lesions in representative area.
- PAS item 5a: Pruriginous lesions with excoriations/crusts
- PAS item 5b: Healed prurigo lesions

PAS items will be summarized as a categorical or continuous variable at each analysis visit, respectively. Absolute change from Baseline for continuous parameter PAS item 4 will also be presented in the summary on the ITT and PP population.

The proportion of subjects with pruriginous lesions with excoriation/crusts (PAS item 5a = 0-25%) and of subjects with healed lesion stages (PAS item 5b = 76-100%) will be presented using non-responder approach. The estimate of treatment unadjusted and strata-adjusted proportion differences with the corresponding two-sided 95% CI, and p-values from the CMH test will be presented.

Absolute and percentage change from Baseline in PAS item 4 will be analyzed using ANCOVA with MI assuming MAR approach for missing data, including treatment group, analysis center and body weight at randomization cut-off (< 90 kg and \geq 90 kg) as factor and baseline as covariate. The least squares means (LSMeans), standard error of LSMeans, and 95% CI for change from baseline, as well as the difference in LSMeans between the treatment groups, the two-sided 95% CI, and associated p-value will be presented for ITT and PP population.

Additionally, the proportion of subjects with number of pruriginous lesions (PAS item 2) $<$ 20 (Responder) will be presented using missing as non-responder for ITT population up to Week 24.

This document is confidential.

10.3.3. Pruritus Numeric Rating Scale (NRS)

The Pruritus NRS is a scale to be used by the subjects to report the intensity of their pruritus (itch) during the last 24 hours. Peak pruritus (PP NRS) is an assessment of the maximum itch intensity in that period while average pruritus (AP NRS) provides a measure of overall pruritus intensity.

Subjects will be asked the following question:

- For maximum itch intensity (PP NRS): "On a scale of 0 to 10, with 0 being 'no itch' and 10 being the 'worst itch imaginable', how would you rate your itch at the worst moment during the previous 24 hours?"
- For average itch intensity (AP NRS): "On a scale of 0 to 10, with 0 being 'no itch' and 10 being the 'worst itch imaginable', how would you rate your itch overall during the previous 24 hours?"

The screening PP/AP NRS will be determined by a single assessment using the PP/AP NRS (score ranging from 0 to 10) for the 24-hour period immediately preceding the screening visit.

The Baseline PP/AP NRS will be determined based on the average of daily PP/AP NRS (score ranging from 0 to 10) respectively during the 7 days immediately preceding Baseline (rounding to nearest whole number is not permitted). A minimum of 4 daily scores out of the 7 days immediately preceding Baseline (up to one day before date of first treatment) is required for this calculation. If there are less than 4 non-missing assessments in the baseline diary window, the interval lower bound can be extended up to 7 additional days, one day at a time, to obtain the most recent 4 non-missing values.

PP/AP NRS at all follow-up visits will be determined in the same manner, however if the intake date of rescue therapy is before and on the last day of the weekly visit window, this week will be treated as treatment failure except for OC analysis and the weekly average will be imputed using the worst case value, see [Section 8.3](#).

Subjects will receive instructions on how to record their PP/AP NRS scores and will complete the assessment once daily in the evening throughout the clinical study (including the run-in and the follow-up period).

PP NRS will be determined by an average as described above at every week from Baseline to Week 24 as a continuous variable.

Descriptive summary of PP NRS will be provided on the ITT and PP populations using observed cases. Absolute change and percentage change from Baseline for the PP NRS will also be included in the summary on the ITT and PP populations.

AP NRS will be determined by an average as described above at every week from Baseline to Week 24 as a continuous variable. Descriptive summary of AP NRS will be provided on the ITT population. Absolute change and percent change from Baseline for the AP NRS score will also be included in the summary.

Absolute and percentage change from Baseline in PP/AP NRS will be analyzed using ANCOVA with MI assuming MAR for missing data including treatment group, analysis center and body weight at randomization cut-off (< 90 kg and \geq 90 kg) as factor and baseline as covariate, and using MMRM, including visit, treatment group, analysis center and body weight at randomization cut-off (< 90 kg and \geq 90 kg) as factor, baseline, the interaction term between baseline and visit, and the interaction term between treatment group and visit as covariates on ITT population. The least squares means (LSMeans), standard error of

This document is confidential.

LSMeans, and 95% CI for change from baseline, as well as the difference in LSMeans between the treatment groups, the two-sided 95% CI, and associated p-value will be presented.

Proportion of subjects with PP NRS at each analysis visit will be summarized:

- Improvement ≥ 4 from baseline
- < 2 at visit
- < 3 at visit

Proportion of subjects with AP NRS at each visit will be summarized:

- Improvement ≥ 4 in change from baseline
- < 2 at visit

The proportions of subjects will be presented on the ITT population using OC and non-responder for AP NRS and using OC, non-responder and LOCF for PP NRS. The estimate of treatment unadjusted and strata-adjusted proportion differences with the corresponding two-sided 95% CI, and p-values from the CMH test will be presented using non-responder.

Line plots for proportion of subjects with PP NRS improvement ≥ 4 and proportion of subjects with PP NRS < 2 using non-responder imputation will be presented on the ITT and PP population.

Additionally the weekly average PP NRS will be recalculated by using at least 2 assessments, or 3 assessments, instead of at least 4 assessments and without extending the visit window for sensitivity analysis.

The proportion of subjects with the weekly average PP NRS using 2, or 3 assessments, will be summarized at each analysis visit:

- PP NRS Improvement ≥ 4 from baseline
- PP NRS < 2

In addition, proportion of subjects with PP NRS improvement ≥ 4 from baseline and IGA success (see [Section 10.3.1](#)) at Week 16, Week 20, and Week 24 will be summarized on the ITT and PP population. The proportion of subjects will be presented using OC, non-responder and LOCF. The estimate of treatment unadjusted and strata-adjusted proportion differences with the corresponding two-sided 95% CI, and p-values from the CMH test will be presented.

Line plots for the change and percentage change from Baseline in PP NRS using OC on the ITT population will also be presented.

10.3.4. Sleep Disturbance Numeric Rating Scale (SD NRS)

The SD NRS is a scale to be used by the subjects to report the degree of their sleep loss related to PN.

The Baseline SD NRS will be determined based on the average of daily SD NRS (score ranging from 0 to 10) during the 7 days up to the treatment start (including until treatment start time) (rounding to nearest whole number is not permitted). A minimum of 4 daily scores out of the 7 days up to Baseline study day is required for this calculation. SD NRS at all following visits will be determined following the rules described in [Table 8-2](#). If there are less than 4 non-missing assessments in the baseline diary window, the interval lower bound can be extended up to 7 additional days, one day at a time, to obtain the most recent 4 non-missing values.

This document is confidential.

Subjects will be asked the following question:

- “On a scale of 0 to 10, with 0 being ‘no sleep loss related to the symptoms of my skin disease (prurigo nodularis)’ and 10 being ‘I did not sleep at all due to the symptoms of prurigo nodularis’, how would you rate your sleep last night?”

Summary using OC will be provided on the ITT population. Absolute change and percentage change from Baseline will also be included in the summary.

Absolute and percentage change from Baseline at each analysis visits will be analyzed using ANCOVA with MI assuming MAR for missing data including treatment group, analysis center and body weight at randomization cut-off (< 90 kg and \geq 90 kg) as factor and baseline as covariate, and using MMRM, including visit, treatment group, analysis center and body weight at randomization cut-off (< 90 kg and \geq 90 kg) as factor, baseline, the interaction term between baseline and visit, and the interaction term between treatment group and visit as covariates on ITT population. The LSMeans, standard error of LSMeans, and 95% CI for change from baseline, as well as the difference in LSMeans between the treatment groups, the two-sided 95% CI, and associated p-value will be presented. Improvement in SD NRS will be calculated using Baseline as the reference point for change in SD NRS score.

The proportion of subjects with an improvement of SD NRS \geq 4 will be summarized using OC and non-responder imputation on ITT population. The estimate of treatment unadjusted and strata-adjusted differences with the corresponding two-sided 95% confidence intervals, and p-values from the CMH test will be presented using non-responder imputation on ITT population.

Line plot for proportion of subjects with SD NRS improvement \geq 4 using non-responder imputation will be presented on the ITT population.

Additionally the proportions of subjects with an improvement of SD NRS \geq 4 from Baseline will be summarized by using at least 2 assessments, or 3 assessments, for calculation of weekly average SD NRS for sensitivity analysis. Proportions are summarized using non-responder imputation on ITT population.

10.3.5. Subject Sleep Diary

Subjects will be given a morning sleep diary (MSD) to record the quality of their sleep. The subject sleep diary is a modification of the consensus sleep diary and is designed to gather information about the subject's sleep pattern and how symptoms related to PN (e.g., itching, burning) affect their sleep.

Subjects will be instructed to complete the sleep diary (Questions 1 to 11) once daily in the morning (i.e., within 1 hour of getting out of bed), with the daily SD NRS. If a subject does not complete the sleep diary in the morning before a scheduled visit, the subject will be allowed to complete the assessment at the clinic visit.

The Baseline sleep diary metrics will be determined based on the average of daily sleep diary metrics respectively during the 7 days data up to the Baseline study day [including until treatment start time] (rounding to nearest whole number is not permitted). A minimum of 4 daily scores out of the 7 days up to Baseline study day is required for this calculation. If there are less than 4 non-missing assessments in the baseline diary window, the interval lower bound can be extended up to 7 additional days, one day at a time, to obtain the most recent 4 non-missing values. Sleep diary metrics at all other visits will be determined following the rules described in [Table 8-2](#).

This document is confidential.

The sleep diary metrics will be derived as below (see **Table 10-3: Sleep Diary Metrics**) using questions in the morning based on morning sleep diary.

Table 10-3: Sleep Diary Metrics

Sleep Parameter	SSD Items Used to Derive the Sleep Parameter
Sleep onset latency (SOL)	Q3
Wakefulness after sleep onset (WASO)	Q5 + Q7
Terminal WASO (TWASO)	Q9 – Q8
Total awake time (TWT)	SOL+ WASO + TWASO
Time in bed (TIB)	Q9 – Q1
Total sleep time (TST)	TIB – TWT
Sleep efficiency (SE)	(TST/TIB)*100
WASO related to PN (WASO-PN)	Q5
Number of WASO related to PN (NWASO-PN)	Q4

Sleep diary metrics will be summarized as continuous variables on observed cases on the ITT population. Change from Baseline in sleep diary metrics will also be summarized.

If Q8 (wake up time) is after Q9 (get out of bed), then Terminal WASO (Q9-Q8) will be set to 0.

If Q8 (wake up time) is before Q1 (get into bed), the time on the next day will be considered for Q9 as only time is collected.

If the duration between Q1 and Q9 is >24 hours, this data will be considered as incalculable and the derived parameters (total awake time and total sleep time) are set to missing.

If total sleep time is negative, it will be considered as missing (not zero) for analysis. The same applies for total awake time.

No hypothesis testing will be performed.

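### The sleep-diary date rule moves only the rising time (Q9) to the next day, so as written total awake time, total sleep time and sleep efficiency are wrong for an ordinary night that crosses midnight

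*SAP*

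**What the plan says.** Table 10-3 in SAP Section 10.3.5 builds the metrics from diary questions. Terminal wake time (TWASO) is Q9 minus Q8, and time in bed (TIB) is Q9 minus Q1. Total awake time (TWT) is "SOL+ WASO + TWASO". Total sleep time (TST) is TIB minus TWT, and sleep efficiency (SE) is TST as a percentage of TIB. Q1 is getting into bed, Q8 waking up and Q9 getting out of bed.

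Four handling rules follow the table:

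- Zero rule: "If Q8 (wake up time) is after Q9 (get out of bed), then Terminal WASO (Q9-Q8) will be set to 0".
- Date rule: if Q8 is before Q1, "the time on the next day will be considered for Q9 as only time is collected".
- Long-interval guard: "If the duration between Q1 and Q9 is >24 hours, this data will be considered as incalculable", and TWT and TST are then set to missing.
- Negative-value rule: "If total sleep time is negative, it will be considered as missing (not zero) for analysis", with the same treatment for TWT.

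Section 5.3 names TWT, TST and SE among seven sleep-diary secondary endpoints. Section 10.3.5 and Table 10-1 state that the sleep diary is not hypothesis-tested.

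**The concern.** The date rule is triggered by Q8 but acts on Q9 alone. Q9 enters two formulas, TIB and TWASO. TIB needs the shift, because bedtime and rising fall on different dates. TWASO is a difference between two morning times, so shifting one and not the other adds a full day. TWASO feeds TWT, and TWT feeds TST and SE.

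The trigger is not an odd case. It is met whenever a subject goes to bed before midnight and wakes after it.

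As written, TST would be available only from nights outside that pattern, such as nights with bedtime after midnight. Weekly averages need at least 4 daily values, so a subject who habitually goes to bed before midnight would have no baseline TST and no change from baseline. That loss would depend on bedtime habit and not on diary compliance. TWT would be reported, but at a level 24 h too high on those nights.

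**Working it through.** **Inputs.** Formulas and rules are from Section 10.3.5. The SAP gives no numerical example, so there is no stated figure to reproduce. The clock times below are assumptions for illustration.

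**Example.** Q1 = 23:00, Q8 = 06:00, Q9 = 06:30, sleep onset latency (SOL) 0.5 h, wakefulness after sleep onset (WASO) 1.0 h. Q8 is before Q1 on the clock, so the date rule applies. Times are in hours from midnight of the bedtime date.

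| Quantity | As written (Q9 = 30.5, Q8 = 6.0) | Both moved (Q9 = 30.5, Q8 = 30.0) |
|---|---|---|
| TIB = Q9 - Q1 | 30.5 - 23.0 = 7.5 h | 7.5 h |
| TWASO = Q9 - Q8 | 30.5 - 6.0 = 24.5 h | 30.5 - 30.0 = 0.5 h |
| TWT = SOL + WASO + TWASO | 0.5 + 1.0 + 24.5 = 26.0 h | 2.0 h |
| TST = TIB - TWT | 7.5 - 26.0 = -18.5 h, set to missing | 5.5 h |
| SE = 100 × TST / TIB | missing, or 100 × (-18.5) / 7.5 = -247% if computed first | 100 × 5.5 / 7.5 = 73% |

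**General result.** Suppose the rule applies and Q9 is at or after Q8 on the clock. TIB is correct, TWASO and TWT equal their true values plus 24 h, and TST equals its true value minus 24 h. True TST is below 24 h, so TST as written is always negative.

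A simulation of 200,000 nights agrees. It assumed bedtimes from 20:00 to 24:00, waking from 03:00 to 10:00 and rising 0 to 2 h later. TST was negative in 100% of nights, TWT was negative in none, and the long-interval guard fired in none.

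**Do the other rules catch it?**

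- The zero rule needs Q8 after Q9. Once Q9 is a day later, that cannot happen.
- The long-interval guard looks at Q1 to Q9, which is 7.5 h here. It does not look at Q8 to Q9.
- The negative-value rule removes TST. TWT of 26.0 h is positive and stays in the summary.

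**A night that is not affected.** Bed 00:30, wake 06:30, up 07:00, same SOL and WASO: the date rule does not apply, TIB = 6.5 h, TWT = 0.5 + 1.0 + 0.5 = 2.0 h, TST = 4.5 h. This is correct.

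**Effect on weekly averages.** For a subject whose diary nights all meet the trigger, at baseline and later, the extra 24 h in TWT is constant and cancels in the change from baseline; only the level is wrong. For a subject whose bedtime sometimes passes midnight, each night that changes side moves a 7-day mean of TWT by 24 / 7 = 3.4 h.

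**The case against.** The strongest reply is that no sensible programmer would apply the sentence this way. Its stated reason, "as only time is collected", shows that it is there to repair a midnight rollover, and its trigger already assumes that waking falls on the day after bedtime. Two benign readings are available: Q8 and Q9 are both next-day times, or the shift serves time in bed only and TWASO uses the two morning clock times. Both give the right answer (5.5 h of sleep in the example). The literal result would also be conspicuous, with awake times above 24 h and most sleep times missing. Section 17 requires review of program logic and output, and the diary data and weekly metrics are listed (listings 16.2.6.5.1 and 16.2.6.5.2).

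Much of this stands. One of the benign readings is probably what was meant, and a silently wrong report is unlikely. But neither reading is in the text. Section 10.3.5 nowhere moves Q8 and nowhere limits the shift to time in bed. Quality control may lead a programmer to repair the rule, but the derivation actually used would then be undocumented, and a second programmer following the SAP would get different values.

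A reader might infer that every night with bedtime before midnight is affected, or that the whole sleep diary is compromised. The SAP does not support either. The trigger also needs waking after midnight. SOL, WASO, PN-related WASO and its count use only Q3, Q4, Q5 and Q7, so they are unaffected.

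**Conclusion.** The written date rule is wrong for nights with bedtime before midnight and waking after it: TWT is 24 h too large and kept, TST is 24 h too small and always set to missing, and SE is lost or invalid. The conclusion rests on one reading: only Q9 is moved, and the moved Q9 is used wherever Q9 appears. That is what the sentence and Table 10-3 say.

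The reach is limited to three of the seven sleep-diary endpoints in Section 5.3. These are summarized descriptively on observed cases. A reader might infer that the efficacy conclusions or the SD NRS key secondary endpoints are at risk. They are not: the SD NRS is a separate daily rating that uses none of these times, and the sleep-diary metrics are outside the testing sequence in Section 10. Nor does the SAP show that any output was produced under the literal reading. This is a specification error to correct before programming is finalized.

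**What to change.** Replace the date rule with:

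> If Q8 is earlier than Q1 on the clock, take both Q8 and Q9 as next-day times. Otherwise, if Q9 is earlier than Q1, take Q9 alone as a next-day time.

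Apply the shift first, then the zero rule, the long-interval guard and the negative-value rule, all with their present content. The second clause covers a subject who goes to bed and wakes before midnight but rises after it. The current trigger misses that case, and TIB comes out negative.

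Q8 and Q9 should move together when Q8 triggers the rule. Testing each time separately against Q1 looks simpler, but Q9 minus Q1 could then never exceed 24 h and the guard would be dead. Take an inconsistent entry of Q1 06:00, Q8 05:00, Q9 07:00. Moving both gives 31 - 6 = 25 h in bed, which the guard rejects as it does now. Separate tests would leave Q9 at 07:00 and accept 7 - 6 = 1 h in bed.

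One small cost remains: under the second clause, a rising time mistyped as slightly before an after-midnight bedtime would be read as a next-day time and pass the guard, so such entries merit a data query. It would also help to state that SE is missing whenever TST is missing. The change is a replaced rule of two sentences and a note on order. It needs no new data and alters no hypothesis.

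### Read literally, the negative-sleep-time rule in SAP 10.3.5 drops a night from total sleep time and sleep efficiency but leaves it in total awake time

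*SAP*

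**What the plan says.** Table 10-3 in SAP section 10.3.5 defines TWT as "SOL+ WASO + TWASO", that is, sleep onset latency plus wakefulness after sleep onset plus terminal wakefulness. TIB is Q9 minus Q1, TST is TIB minus TWT, and SE is TST as a percentage of TIB. If the reported wake-up time falls after the time of leaving bed, "then Terminal WASO (Q9-Q8) will be set to 0".

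Two rules then handle implausible values. When the span from Q1 to Q9 exceeds 24 hours, "the derived parameters (total awake time and total sleep time) are set to missing". For negative values the text is: "If total sleep time is negative, it will be considered as missing (not zero) for analysis. The same applies for total awake time". Neither rule names SE.

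The metrics are averaged over a week. For baseline, "A minimum of 4 daily scores out of the 7 days up to Baseline study day is required for this calculation", and the window may be extended backwards by up to 7 days if this is not met. On the analysis: "Sleep diary metrics will be summarized as continuous variables on observed cases on the ITT population", and "No hypothesis testing will be performed".

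**The concern.** TST, TWT and SE describe the same night and are tied together by TST + TWT = TIB. A rule that removes a night from one should say what happens to the other two. Here the sentence about TWT seems meant to do that, but its literal condition, a negative TWT, cannot arise. The problem on such a night is a TWT that is too large.

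At stake is whether three listed secondary endpoints (SAP section 5.3) rest on the same nights. If they do not, their weekly means cannot be reconciled, and two programmers could produce different TWT tables from the same data.

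**Working it through.** The SAP gives no figure for this point, so there is none to reproduce. The check applies the Table 10-3 formulas to assumed diary entries.

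**Step 1: can TWT be negative?** TWT = Q3 + Q5 + Q7 + max(Q9 − Q8, 0). Every term is zero or more, so it cannot. As a logic check, a grid of 3125 invented entries was run: five values each for Q3, Q5 and Q7 from 0 to 4 h, five clock times each for Q8 and Q9, and one bedtime. It gave TWT < 0 in 0 entries and TST < 0 in 895. These counts test the logic and are not expected frequencies.

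**Step 2: what triggers the TST rule?** TST = TIB − TWT < 0 if and only if TWT > TIB. SE = 100 × TST/TIB has no input once TST is missing, so its loss follows by derivation and is not written.

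**Step 3: an assumed week.** TIB is 8 h every night. An ordinary night has TWT 3.5 h, TST 4.5 h and SE 56.25%. An affected night has Q3 = 3, Q5 = 4, Q7 = 1 and terminal wakefulness 0.5 h, so TWT = 8.5 h and TST = −0.5 h. With k affected nights out of 7, the literal rule gives mean TWT = [3.5(7 − k) + 8.5k]/7.

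| k | Literal: TST / TWT / sum (h) | TWT also missing: TST / TWT (h) | TWT capped at TIB: TST / TWT (h), SE |
|---|---|---|---|
| 0 | 4.50 / 3.50 / 8.00 | 4.50 / 3.50 | 4.50 / 3.50, 56.25% |
| 1 | 4.50 / 4.21 / 8.71 | 4.50 / 3.50 | 3.86 / 4.14, 48.2% |
| 2 | 4.50 / 4.93 / 9.43 | 4.50 / 3.50 | 3.21 / 4.79, 40.2% |
| 3 | 4.50 / 5.64 / 10.14 | 4.50 / 3.50 | 2.57 / 5.43, 32.1% |

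Under the literal rule, SE stays at 56.25% throughout while TWT rises, and TST + TWT exceeds the 8 h in bed. Under either consistent rule the sum is 8 h.

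**Step 4: the four-night minimum.** At k = 4 only three TST nights remain, while TWT still has seven (mean 6.36 h). At baseline, TST and SE could then draw on an extended window that TWT does not need. In a week without an extension, if the same minimum applies, TST is missing and TWT is reported.

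**Step 5: not every negative TST is a bad night.** Only clock times are collected, and Q9 moves to the next day only when Q8 is before Q1. Assume in bed at 22:00, last awakening at 23:30, out of bed at 06:00. Q8 is not before Q1, so on the rule as written TIB = 6 − 22 = −16 h. TST is then negative whatever the sleep was. Capping TWT at this TIB would set TWT to −16 h, so a cap is safe only where TIB is positive and correctly dated.

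**Step 6: possible size.** None of these inputs is in the SAP. Assume nightly TST is normal with mean μ = 3 h at baseline and 6 h on effective treatment, and night-to-night SD s. Dropping negative nights gives a mean of μ + s·φ(μ/s)/Φ(μ/s). A zero floor gives μ·Φ(μ/s) + s·φ(μ/s).

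- s = 2.0 h: 7% of baseline nights negative; improvement 2.73 h (drop) against 2.94 h (floor), 7% smaller.
- s = 2.5 h: 12% negative; 2.51 h against 2.87 h, 13% smaller.
- s = 3.0 h: 16% negative; 2.30 h against 2.78 h, 17% smaller.
- s = 1.5 h: about 2% negative, and the effect is small.

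**The case against.** The strongest reply is that the TWT sentence should be read so that it does something: a night with negative TST is missing for TWT as well. The 24-hour rule just before it sets both to missing together. On that reading the split does not occur. This stands as a plausible intention, so a reader who concludes that the SAP definitely keeps these nights in TWT goes too far. But the SAP does not state that intention, and the literal condition is a negative TWT.

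A reader might also infer that the worst nights vanish and that the treatment effect is understated by 7% to 17%. The documents do not support that. A coherently reported sleepless night has TWT = TIB, so TST = 0, and it stays in. There is thus no conflict with the top anchor of the sleep disturbance scale in section 10.3.4, "I did not sleep at all due to the symptoms of prurigo nodularis". Only impossible values are removed, and some of them will be entry or dating errors. The percentages come from assumed means and SDs under a normal model that itself generates the negative values, and they are measured against a zero floor, not a known truth.

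Treating an impossible entry as missing is defensible. What remains is that the treatment must be the same for all three metrics, and that some genuinely very poor nights with over-reported wakefulness may be among those removed.

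**Conclusion.** The point holds as a defect of specification. The TWT sentence has no effect as written, and SE has no rule of its own. Under the literal reading, the weekly means of TST and SE rest on different nights from the mean of TWT, and TST + TWT exceeds time in bed. That follows from Table 10-3 and the terminal-wakefulness floor and needs no outside assumption. The hours in the example week do rest on assumed entries.

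The direction and size of any bias in the treatment comparison are unknown from the SAP: illustratively, from small to about 17% of the improvement in TST under the stated assumptions. The consequence is limited. These are secondary endpoints summarised descriptively on observed cases without a test, and no primary or key secondary endpoint uses this derivation. It is a minor point, worth correcting because the correction is cheap.

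**What to change.** Replace the two sentences on negative values in section 10.3.5 with one rule: on any night where TWT exceeds TIB (equivalently, TST is negative), TWT, TST and SE are all set to missing, so that the three metrics use the same nights. Name SE in the 24-hour rule too. Report the number of nights excluded in this way by arm and visit.

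Because some of these nights may be genuinely very poor ones, add a supporting summary in which TWT is capped at TIB, giving TST = 0 and SE = 0. Limit it to nights with a positive, correctly dated TIB.

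The cost is one sentence, one derivation line, a count and one extra descriptive summary. The drawback is that some real wakefulness leaves the main TWT summary; the count and the capped summary show how much that could matter.
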